7.4.1.2 Dose Delay Criteria for Cabozantinib

Cabozantinib dosing should be delayed for the following:

- Urine protein/creatinine ratio (UPCR) > 2.0 *or* urine dipstick protein \geq 3+ *or* urine protein > 2.0 g / 24 hours. Obtain 24 hour urine protein prior to next dosing visit.
- Grade 3 prolonged QTc interval (ie, QTcF interval > 500 msec on at least 2 out of 3 separate ECGs performed at least 3 minutes apart)
- Any Grade 2 or 3 drug-related venous thrombosis requiring anticoagulation, with the following exception:
 - Any recurrent or worsening venous thromboembolic event after restarting cabozantinib will require discontinuation
- Any other Grade 2 drug-related adverse event or grade 2 drug-related laboratory abnormality (e.g., AST, ALT, total bilirubin) that persists for more than 1 week or worsens despite supportive care management, with the following exception:
 - Any Grade 2 drug-related hemorrhage requires dose delay
 - Grade \geq 2 arterial thromboembolic events, including cerebrovascular ischemia, cardiac ischemia/infarction, peripheral or visceral arterial ischemia, require discontinuation
- Sustained Grade 3 drug-related hypertension (systolic BP \geq 160 mm Hg or diastolic BP \geq 100 mm Hg). NOTE: Stopping or reducing the dose of cabozantinib is expected to cause a decrease in BP. The treating physician should monitor the participant for hypotension and adjust the number and dose of antihypertensive medications accordingly.
- Any other Grade 3 drug-related adverse event or laboratory abnormality, with the following exceptions:
 - Grade \geq 3 drug-related hemorrhage requires discontinuation ([Section 8.1.2](#)).
 - Drug-related AST or ALT > 8 x ULN requires discontinuation ([Section 8.1.2](#)).
 - Concurrent AST or ALT > 3 x ULN and total bilirubin > 2 x ULN, consistent with potential drug-induced liver injury (see [Section 9.2.7](#)), requires discontinuation ([Section 8.1.2](#))
 - Grade 3 drug-related amylase or lipase abnormalities that are not associated with symptoms or clinical manifestations of pancreatitis do not require dose delay. In such cases, more frequent monitoring (eg, weekly) of amylase and lipase is recommended. If amylase or lipase worsen to Grade 4 severity or the participant develops symptoms or clinical manifestations of pancreatitis, dosing should be delayed.

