- Grade 4 drug-related amylase or lipase abnormalities require dose delay. Participants should be monitored for development of symptoms or clinical manifestations of pancreatitis.
- Grade 4 drug-related electrolyte abnormalities require dose delay. Electrolyte correction with supplementation/appropriate management should be promptly initiated.

- Grade 4 drug-related neutropenia, lymphopenia, leukopenia, anemia, or thrombocytopenia
- Any adverse event, laboratory abnormality, or intercurrent illness which, in the judgment of the investigator, warrants delaying cabozantinib dosing
- For participants scheduled for major surgery, including dental surgery which may impact bone healing, cabozantinib dosing should be delayed at least 28 days prior to scheduled surgery. The treating physician should use clinical judgment with regard to the risks and benefits of the planned surgical procedure if it is not possible to delay cabozantinib dosing for 28 days prior to the procedure. A delay of cabozantinib dosing of 5 to 7 days is recommended for healing for minor surgery.

As a general approach, all AEs related to cabozantinib should be managed with supportive care when possible at the earliest signs of toxicity. Calcium, magnesium, potassium, and phosphorus should be kept above the lower limits of the laboratory normal values. Please refer to the cabozantinib IB, [Appendix 10](#), and [Appendix 11](#) for additional information regarding dose modifications and AE management.²¹

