7.4.2.2 Dose Reduction and Escalation for Cabozantinib

Dose reductions and dose escalations for adverse event management are allowed for cabozantinib (Table 7.4.2-1). Cabozantinib doses will not be re-escalated once reduced, unless a concomitant strong CYP3A4 inducer is started (see below). The only exception is participants who continue on cabozantinib alone after discontinuation of nivolumab alone (Arm A) or discontinuation of both nivolumab and ipilimumab (Arm B) who may re-escalate one dose level if the prior dose reduction was due to a toxicity felt by the investigator to have been mainly related to nivolumab and/or ipilimumab.

After toxicity requiring a dose delay has improved and meets the criteria to resume dosing (Section 7.4.3.2), participants who were receiving cabozantinib 40 mg daily prior to the delay will resume cabozantinib at 20 mg daily. Participants who were receiving cabozantinib 20 mg daily prior to the delay and require another dose delay will resume cabozantinib at 20 mg every other day. If more than 2 dose reductions are necessary (ie, reduction to less than 20 mg every other day), cabozantinib must be permanently discontinued (Section 8.1.2).

Participants who required a dose delay due to Grade 3 hypertension, which improved with antihypertensive medications, or any Grade 2 or 3 drug-related adverse event or asymptomatic laboratory abnormality that improved to Grade ≤ 1 within 7 days with supportive medical care may resume cabozantinib at the same dose or a reduced dose, at the discretion of the investigator.

Participants with asymptomatic Grade 2 drug-related AST, ALT or total bilirubin elevation, or Grade 3 drug-related lipase or amylase abnormalities that are not associated with symptoms or clinical manifestations of pancreatitis may reduce cabozantinib by one dose level, without delaying dosing, at the discretion of the investigator. See also section 7.4.1.2.

In Participants Who Start Taking a Concomitant Strong CYP3A4 Inhibitor: Reduce the daily cabozantinib dose by 20 mg (for example, from 40 mg to 20 mg daily). Resume the dose that was used prior to initiating the CYP3A4 inhibitor 2 to 3 days after discontinuation of the strong inhibitor (see Prescribing Information for cabozantinib).

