7.4.3.2 Criteria to Resume Cabozantinib Treatment

Participants may resume treatment with cabozantinib when the drug-related AE(s) resolve to Grade \leq 1 or baseline value, with the following exceptions:

- Participants may resume dosing in the presence of Grade 2 fatigue
- Participants who delayed dosing due to prolonged QTcF may resume dosing at one reduced dose level once QTcF returns to \leq 500 msec
- Participants who delayed dosing due to UPCr $>$ 2.0 or urine dipstick protein \geq 3+ or urine protein $>$ 2.0 g / 24 may resume dosing at one dose level reduction when UPCr is \leq 2.0 or 24 hour urine protein \leq 2.0 g /24
- Participants who delayed dosing due to Grade 3 hypertension may resume dosing at the same dose or at one dose level reduction, at the discretion of the investigator, when hypertension has improved to Grade \leq 2
- Participants who delayed dosing due to Grade 4 lipase or amylase abnormalities may resume dosing upon resolution to Grade \leq 2
- Participants who delayed dosing due to major surgery should not resume cabozantinib until complete wound healing has taken place. Following cabozantinib resumption, participants should be monitored for wound dehiscence, wound infections, and other signs of impaired wound healing.
- Participants who develop a pulmonary embolism and/or DVT should have study treatment interrupted until therapeutic anticoagulation is established. Treatment with cabozantinib may be resumed in subjects with pulmonary embolism or DVT if it is determined that the event is uncomplicated and that the subject is deriving clinical benefit from cabozantinib treatment and that anticoagulation does not place them at a significant risk that outweighs the benefit of resuming treatment per discretion of the investigator.
- Participants who delayed dosing due to \leq Grade 2 hemorrhage may resume dosing if bleeding is under control (recovered to at least Grade 1 level) and has a low risk of recurrence
- If treatment is delayed $>$ 6 weeks for any reason, the participant must be permanently discontinued from study therapy, except in cases where permission to resume treatment is granted by the BMS Medical Monitor or designee.

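### Read literally, the cabozantinib delay rule stops dosing for a persistent Grade 2 amylase or lipase rise but not for an asymptomatic Grade 3 rise; the related statements need reconciling

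*Protocol*

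**What the plan says.** All of these are in the protocol and concern cabozantinib.

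- **Grade 2, Section 7.4.1.2.** Apart from the conditions given their own bullets, dosing should be delayed for a Grade 2 drug-related adverse event or a "grade 2 drug-related laboratory abnormality (e.g., AST, ALT, total bilirubin) that persists for more than 1 week", or that worsens despite supportive care. Two exceptions are listed beneath. One is that "Any Grade 2 drug-related hemorrhage requires dose delay". The other sends arterial thromboembolic events of Grade 2 or higher to discontinuation.
- **Grade 3, Section 7.4.1.2.** Other Grade 3 drug-related events and laboratory abnormalities call for delay, but "Grade 3 drug-related amylase or lipase abnormalities that are not associated with symptoms or clinical manifestations of pancreatitis do not require dose delay". Closer monitoring is recommended and no time limit is set. Delay applies if the value reaches Grade 4 or pancreatitis becomes clinically apparent.
- **Grade 4, Section 7.4.1.2.** "Grade 4 drug-related amylase or lipase abnormalities require dose delay".
- **Reducing without delaying, Section 7.4.2.2.** The investigator may drop one dose level without a hold for "Participants with asymptomatic Grade 2 drug-related AST, ALT or total bilirubin elevation, or Grade 3 drug-related lipase or amylase abnormalities", the latter when there is no clinical sign of pancreatitis. Grade 2 amylase or lipase is not named.
- **Restarting, Section 7.4.3.2.** The general rule is that "Participants may resume treatment with cabozantinib when the drug-related AE(s) resolve to Grade" 1 or lower, or to baseline. A separate exception says "Participants who delayed dosing due to Grade 4 lipase or amylase abnormalities may resume dosing upon resolution to Grade" 2 or lower.

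**The concern.** A delay rule for a graded laboratory value should not become less strict as the value gets worse. Here the general Grade 2 bullet is worded openly enough to take in amylase and lipase, while the exemption for values without pancreatitis symptoms is attached to Grade 3 alone. A site that follows the text literally would hold for the milder result and carry on dosing through the worse one.

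What is at stake is cabozantinib exposure in Arm A and consistency between sites. One site may apply the general bullet as written. Another may infer that amylase and lipase only matter from Grade 3 upward. SAP Sections 7.4.1 and 7.4.2.4 report cabozantinib dose intensity, holds and reductions, so a difference in reading would carry into those tables.

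**Working it through.** There is no sample-size, power or alpha figure to reproduce. The check sets the rules side by side for a drug-related amylase or lipase rise without symptoms of pancreatitis.

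| State | Delay (7.4.1.2) | Reduce without delay (7.4.2.2) | Level for restart (7.4.3.2) |
|---|---|---|---|
| Grade 2, over 1 week or worsening despite supportive care | Yes, through the general bullet | Not named | Grade 1 or lower, or baseline |
| Grade 3, any duration | Not required | Allowed, investigator's discretion | No hold required |
| Grade 4 | Yes | Not named | Grade 2 or lower |

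**Step 1: does the Grade 2 bullet reach amylase and lipase?** The liver tests in it are introduced as examples, so they do not close the list. The bullet covers what the preceding bullets leave over, and those deal with proteinuria, QTc prolongation and venous thrombosis. Its own exceptions are hemorrhage and arterial events. Nothing takes amylase or lipase out.

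**Step 2: does another section take them out?** Section 7.4.2.2 offers reduction in place of delay for Grade 2 liver tests and asymptomatic Grade 3 amylase or lipase, but not for Grade 2 amylase or lipase. Section 8.1.2 mentions them only at Grade 4, for discontinuation. The investigator-judgment bullet in Section 7.4.1.2 can add a delay but does not waive one. So the required action by rising grade is delay, none, delay.

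**Step 3: where two instructions meet in one participant.**
- *Grade 2 worsening to Grade 3 without symptoms, despite supportive care.* The worsening limb of the Grade 2 bullet calls for delay; the Grade 3 exemption says none is required.
- *Grade 4 improving to Grade 2.* Section 7.4.3.2 allows restart. If the value stays at Grade 2 for more than a week, the Grade 2 bullet calls for delay again.

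**Step 4: the restart levels differ.** A participant held at Grade 4 may restart at Grade 2. A participant held at Grade 2 and unchanged may not, unless Grade 2 was the baseline value. Under Sections 7.4.3.2 and 8.1.2, a hold beyond 6 weeks means permanent discontinuation unless the Medical Monitor agrees otherwise.

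**Step 5: what a Grade 2 hold can cost.** Under Section 7.4.2.2, a Grade 2 laboratory abnormality that improves to Grade 1 or lower within 7 days may restart at the same dose. Otherwise the default is one level down: 40 mg daily to 20 mg daily, then to 20 mg every other day. A need for a further reduction means discontinuation. One slow Grade 2 hold can therefore use one of the two permitted reductions.

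**Step 6: can the trigger arise in routine conduct?** Table 2-2 schedules amylase and lipase at Cycles 1, 2, 4, 5, 7 and 10, then every 3 cycles, with 2-week cycles. The gaps are (2−1)×2 = 2 weeks, (4−2)×2 = 4, (5−4)×2 = 2, (7−5)×2 = 4 and (10−7)×2 = 6. Two consecutive scheduled Grade 2 results therefore span at least 2 weeks, which is over 1 week if the value stayed at Grade 2 in between. The trigger is reachable; how often is not stated.

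**The case against.** The best reply is that the specific statements should govern the general one. No sentence says Grade 2 amylase or lipase must be held; the general bullet's examples are all liver tests. Wherever amylase and lipase are named for cabozantinib, action begins at Grade 3 or 4. Section 7.4.2.2 pairs Grade 2 for liver tests with Grade 3 for lipase and amylase, and Section 7.4.3.2 accepts Grade 2 for restart after Grade 4. Read that way the scheme is coherent. Section 7.4.1.2 also sends sites to the cabozantinib investigator brochure, which is not available here and may cover the point.

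Much of this is fair as evidence of intent, but it does not settle the text. The specific delay statements address Grades 3 and 4, so none covers Grade 2 that could displace the general bullet. The restart exception is confined to participants held for Grade 4. The protocol states no rule that specific bullets prevail.

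Four stronger readings are tempting and are not supported.

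- *Sunitinib has the same defect.* Its Grade 2 bullet in Section 7.4.1.3 refers only to adverse events, with no laboratory wording and no 1-week term, although its Grade 3 bullet does mention laboratory abnormalities. The Appendix 3 definition of an adverse event can include an abnormal laboratory finding, so the sunitinib text is open to question, but it does not contain this contradiction.
- *The same result generally gets opposite actions.* Each grade taken alone has one stated delay rule. The direct clashes are the two sequences in Step 3.
- *Any Grade 2 value lasting 8 days must be held, while Grade 3 leaves dosing untouched.* The Grade 2 rule applies only to drug-related abnormalities and carries a supportive-care qualifier. At Grade 3 the investigator may still reduce the dose.
- *The rule lowers dose intensity in Arm A.* It could, but the documents give no incidence of Grade 2 amylase or lipase rises, and restart at baseline is allowed.

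**Conclusion.** The cabozantinib rules are inconsistent as written. Followed literally, a persistent Grade 2 amylase or lipase rise calls for delay, an asymptomatic Grade 3 rise does not, and Grade 4 does again. Two sequences also put conflicting instructions on one participant. This rests on reading the examples in the Grade 2 bullet as open, on the abnormality being drug-related, on its persisting or worsening despite supportive care, and on the unseen investigator brochure not changing the rule.

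The size per event is bounded by the text: one slow Grade 2 hold can use one of two reductions. The size for the trial is unknown. Efficacy is analyzed as randomized (Protocol Section 10.2), and the hypothesis tests, event targets and error rates do not depend on this rule. It is a clarification worth making for consistent dosing and interpretable exposure data, not a threat to the primary analysis.

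**What to change.** Reconcile the Grade 2, Grade 3 and Grade 4 amylase and lipase statements in Section 7.4.1.2 with the reduce-without-delay option in Section 7.4.2.2 and the restart levels in Section 7.4.3.2. State whether the general Grade 2 laboratory bullet applies to amylase and lipase without symptoms. State also what applies when Grade 2 worsens to Grade 3, and when Grade 2 persists after restart from a Grade 4 hold. The sponsor's clinicians must decide which rule stands; this review proposes none.

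The cost is about one clarifying sentence, with matching cross-references, in an amendment or administrative letter. The document history shows an administrative letter already used to resolve inconsistencies in the original protocol. No change to the SAP is needed.

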7.4.1 Dose Delay Criteria

Dose delay criteria for management of adverse events during nivolumab, ipilimumab, cabozantinib, or sunitinib treatment are outlined in this section.

Dosing of nivolumab (in Arm A) or nivolumab and ipilimumab (in Arm B) may be delayed without delay of cabozantinib dosing if toxicity is felt to be related to only nivolumab (Arm A) or nivolumab and ipilimumab (Arm B) and not related to cabozantinib. Conversely, dosing of cabozantinib may be delayed without delay of nivolumab dosing (in Arm A) or nivolumab and ipilimumab dosing (in Arm B) if toxicity is felt to be related to only cabozantinib and not related to nivolumab (Arm A) or nivolumab and ipilimumab (Arm B). However, if toxicity is considered related to all study drugs or if the investigator is unable to determine which study drug is the cause of the AE, then all study drugs in the combination should be delayed.

Participants who require dose delay should be re-evaluated weekly or more frequently if clinically indicated and resume dosing when re-treatment criteria are met (see Section 7.4.3).

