7.4.1.3 Dose Delay Criteria for Sunitinib

Sunitinib dose delays should be based on instructions in the approved product label and should be considered for any severe or intolerable drug-related adverse events.

Within a cycle, missed doses of sunitinib should be skipped. Participants should never be dosed during the 2-week off period of each 6-week cycle, even if treatment delays occurred earlier in the cycle and therapy is ready to be resumed. If treatment is delayed past the end of the 6-week cycle, the start of the next cycle should be delayed until treatment with sunitinib resumes.

Prior to resuming therapy after a dose delay, refer to [Section 7.4.2](#) for dose reduction recommendations and [Section 8](#) for discontinuation criteria.

For this protocol, sunitinib dosing should be delayed for any of the following:

- Urine protein/creatinine ratio (UPCR) ≥ 2.0 or urine dipstick protein $\geq 3+$ or urine protein ≥ 2.0 g / 24 hours. Obtain 24 hour urine protein prior to next dosing visit.
- Grade 3 prolonged QTc interval (ie, QTcF interval > 500 msec on at least 2 out of 3 separate ECGs performed at least 3 minutes apart)
- Any Grade 2 or 3 drug-related venous thrombosis requiring anticoagulation, with the following exception:
 - Any recurrent or worsening venous thromboembolic event after restarting sunitinib will require discontinuation
- Any other Grade 2 drug-related adverse event that persists or worsens despite supportive care management, with the following exception:
 - Any Grade 2 drug-related hemorrhage requires dose delay
 - Grade ≥ 2 arterial thromboembolic events, including cerebrovascular ischemia, cardiac ischemia/infarction, peripheral or visceral arterial ischemia, require discontinuation
- Grade 3 drug-related hypertension (systolic BP ≥ 160 mm Hg or diastolic BP ≥ 100 mm Hg). NOTE: Stopping or reducing the dose of sunitinib is expected to cause a decrease in BP. The

treating physician should monitor the participant for hypotension and adjust the number and dose of antihypertensive medications accordingly.

- Any other Grade 3 drug-related adverse event or laboratory abnormality, with the following exceptions:
 - Grade \geq 3 drug-related hemorrhage requires discontinuation (Section 8.1.2).
 - Drug-related AST or ALT $>$ 8 x ULN requires discontinuation (Section 8.1.2).

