8 DISCONTINUATION CRITERIA

8.1 Discontinuation from Study Treatment

Participants **MUST** discontinue investigational product (and non-investigational product at the discretion of the investigator) for any of the following reasons:

- Participant's request to stop study treatment. Participants who request to discontinue study treatment will remain in the study and must continue to be followed for protocol specified follow-up procedures. The only exception to this is when a participant specifically withdraws consent for any further contact with him/her or persons previously authorized by participant to provide this information
- Any clinical adverse event (AE), laboratory abnormality or intercurrent illness which, in the opinion of the investigator, indicates that continued participation in the study is not in the best interest of the participant
- Termination of the study by Bristol-Myers Squibb (BMS)
- Loss of ability to freely provide consent through imprisonment or involuntarily incarceration for treatment of either a psychiatric or physical (eg, infectious disease) illness. (Note: Under specific circumstances, and only in countries where local regulations permit, a participant who has been imprisoned may be permitted to continue as a participant. Strict conditions apply and BMS approval is required.)
- Criteria listed in 8.1.1
- Disease progression of RCC or occurrence of a secondary malignancy which requires systemic therapy for treatment

Refer to the Schedule of Activities for data to be collected at the time of treatment discontinuation and follow-up and for any further evaluations that can be completed.

In the case of pregnancy, the investigator must immediately notify the BMS Medical Monitor/designee of this event. In most cases, the study treatment will be permanently discontinued in an appropriate manner (eg, dose tapering if necessary for participant safety). Please call the BMS Medical Monitor within 24 hours of awareness of the pregnancy. If the investigator determines a possible favorable benefit/risk ratio that warrants continuation of study treatment, a discussion between the investigator and the BMS Medical Monitor/designee must occur.

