8.1.2 Cabozantinib Dose Discontinuation

Permanently discontinue cabozantinib for participants with any of the following:

- Any requirement for more than 2 cabozantinib dose reductions (ie, reduction to less than 20 mg every other day)
- Any Grade \geq 2 drug-related arterial thromboembolic events, including cerebrovascular ischemia, cardiac ischemia/infarction, peripheral or visceral arterial ischemia
- Any Grade \geq 3 drug-related hemorrhage
- Grade 4 hypertension or persistent Grade 3 hypertension despite optimal medical management and cabozantinib dose reduction
- Drug-related reversible posterior leukoencephalopathy syndrome

- Development of drug-related fistula or GI perforation
- Drug-related nephrotic syndrome
- Any drug-related liver function test (LFT) abnormality that meets the following criteria requires discontinuation:
 - AST or ALT > 8 x ULN.
 - Concurrent AST or ALT > 3 x ULN and total bilirubin >2 x ULN, consistent with potential drug-induced liver injury (see [Section 9.2.7](#)).
- Any Grade 4 drug-related adverse event or laboratory abnormality, with the following exceptions:
 - Grade 4 neutropenia ≤ 7 days
 - Grade 4 lymphopenia or leukopenia
 - Grade 4 amylase or lipase abnormalities that are not associated with symptoms or clinical manifestations of pancreatitis
 - Isolated Grade 4 electrolyte abnormalities that are not associated with clinical sequelae and are corrected with supplementation/appropriate management within 72 hours of their onset
- Any dosing interruption lasting > 6 weeks unless the BMS Medical Monitor or designee is consulted and agrees with the rationale for resuming therapy after a delay > 6 weeks. Note that tumor assessments should continue as per protocol even if dosing is interrupted.
- Any adverse event, laboratory abnormality, or intercurrent illness which, in the judgment of the Investigator, presents a substantial clinical risk to the participant with continued cabozantinib dosing.

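### Cabozantinib: Protocol 7.4.1.2 lists Grade 4 drug-related anemia and thrombocytopenia as delay events, but 8.1.2 requires permanent discontinuation for both, and the cabozantinib text has no check before restart

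*Protocol*

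**What the plan says.** **Delay.** Protocol 7.4.1.2 includes, as a reason to hold cabozantinib, "Grade 4 drug-related neutropenia, lymphopenia, leukopenia, anemia, or thrombocytopenia". The bullet carries no note that any of these events requires a permanent stop. Elsewhere the same list does carry such notes, for example "Drug-related AST or ALT > 8 x ULN requires discontinuation", with a reference to 8.1.2.

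**Resume.** Section 7.4.1 tells sites to re-evaluate delayed participants and "resume dosing when re-treatment criteria are met (see Section 7.4.3"). Section 7.4.3.2 opens: "Participants may resume treatment with cabozantinib when the drug-related AE(s) resolve to Grade" 1 or lower, or to baseline. Section 7.4.2.2 sets the dose: once the resume criteria are met, "participants who were receiving cabozantinib 40 mg daily prior to the delay will resume cabozantinib at 20 mg daily".

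**Discontinue.** Section 8.1.2 orders permanent discontinuation for "Any Grade 4 drug-related adverse event or laboratory abnormality, with the following exceptions". The exceptions are neutropenia of 7 days or less; lymphopenia or leukopenia; amylase or lipase abnormalities without pancreatitis; and isolated electrolyte abnormalities without sequelae that are corrected within 72 hours. The general list of mandatory discontinuation reasons in 8.1 refers only to "Criteria listed in 8.1.1", which is the nivolumab and ipilimumab section.

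**Sunitinib.** Section 7.4.1.3 contains a sentence that the cabozantinib text does not: "Prior to resuming therapy after a dose delay, refer to" Section 7.4.2 for dose reduction and Section 8 for discontinuation.

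**The concern.** For one drug, one causality and one grade, the protocol names two dispositions: hold in 7.4.1.2, stop for good in 8.1.2. A site that starts at the delay list and follows its references reaches a restart instruction without being sent to 8.1.2 for these two events. At stake is re-exposure, at a reduced dose, of a participant in the experimental arm who has had a Grade 4 drug-related anemia or thrombocytopenia. Each such restart would also be a protocol deviation, and sites could handle the same event differently.

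**Working it through.** The plan gives no figure on this point, so the check sets the sections side by side.

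**Step 1. Each Grade 4 event named in 7.4.1.2 against the exceptions in 8.1.2.**

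| Grade 4 drug-related event in 7.4.1.2 | Exception in 8.1.2 | Can a delay end in restart? |
|---|---|---|
| Amylase or lipase | Yes, if no pancreatitis | Yes, conditionally |
| Electrolytes | Yes, if isolated, no sequelae, corrected within 72 hours | Yes, conditionally |
| Neutropenia | Yes, if 7 days or less | Yes, conditionally |
| Lymphopenia | Yes | Yes |
| Leukopenia | Yes | Yes |
| Anemia | None | No |
| Thrombocytopenia | None | No |

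Named events: 7. With a full or conditional exception: 5. Without: 7 − 5 = 2.

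**Step 2. The route for a participant on 40 mg with Grade 4 drug-related thrombocytopenia.** 7.4.1.2: hold. 7.4.1: go to 7.4.3. 7.4.3.2: restart is allowed at Grade 1 or lower or at baseline; none of its special cases mentions a cytopenia. 7.4.2.2: restart at 20 mg daily. The same-dose option there covers Grade 3 hypertension and Grade 2 or 3 events, so it does not apply. The 8.1.2 route for the same participant is permanent discontinuation. Anemia gives the same result.

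**Step 3. Does the cabozantinib text send the site to 8.1.2 along that route?** References to 8.1.2 by section:

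- 7.4.1: 0
- 7.4.1.2: 3 (Grade 3 or higher hemorrhage; AST or ALT above 8 x ULN; concurrent transaminase and bilirubin elevation)
- 7.4.2.2: 1 (more than 2 dose reductions)
- 7.4.3.2: 0

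Total: 0 + 3 + 1 + 0 = 4. Each is tied to its own trigger. None concerns anemia or thrombocytopenia, and none is a general check before restart. The sunitinib text has 2 general references: the sentence in 7.4.1.3 before resuming, and the reference to 8.1.3 in 7.4.2.3 when a reduction is considered.

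**Step 4. Which rule governs?** Section 8.1.2 is an order; 7.4.3.2 says participants may resume, and the resumption dose in 7.4.2.2 applies only once those criteria are met. Section 7.4 names Section 8 alongside 7.4.1 and 7.4.2 for cabozantinib modifications. The opening of 8.1.1 says discontinuation is assessed separately for each drug, cabozantinib included. Section 9 bars waivers and requires immediate safety concerns to be discussed with the sponsor. None of these ranks the sections or ties the check to the moment of restart, but together they make discontinuation the governing instruction.

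**The case against.** The best answer is that 7.4.1.2 is a hold list and promises no restart. Holding a dose and then stopping for good are compatible steps. The list also delays neutropenia of any duration, any Grade 4 electrolyte abnormality and any Grade 4 amylase or lipase abnormality, and 8.1.2 requires a stop for part of each, again without a note in the bullet. The nivolumab lists overlap in the same way. The resume text is generic and does not name these two events. The cabozantinib Investigator Brochure, which 7.4.1.2 cites for dose modification, is not available here.

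Much of this stands. Overlap between the lists is not an error in itself, and discontinuation is the better reading. What remains is narrower. For the other five events, delay leads to restart in at least some cases that 8.1.2 allows; for these two it never does. Section 7.4.1.2 also marks several of its own entries as requiring discontinuation, so an unmarked entry is naturally read as hold and resume. The brochure limits the claim to the protocol text but does not repair it.

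A reader might infer that the protocol offers two equally valid rules, or permits rechallenge after these events. The documents do not support that: 8.1.2 is mandatory and exemptions are not allowed. A reader might also infer the same practical defect for sunitinib, whose delay list has the same bullet. There the entry is only redundant, because 7.4.1.3 and 7.4.2.3 already send sites to the discontinuation criteria.

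**Conclusion.** The point holds as a minor safety-conduct contradiction. It affects 2 of the 7 Grade 4 events named in the cabozantinib delay list. These are counts of list entries and cross-references, not of participants; the documents give no expected frequency for either event, so the number at risk cannot be estimated. The hazard is limited by the mandatory wording of 8.1.2, the recovery and dose-reduction conditions on any restart, and the duty to consult the sponsor.

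The conclusion rests on the visible protocol text. Some sections are redacted, but those governing cabozantinib delay, resumption and discontinuation can be read. It would be tempting to extend the point to the trial's results; nothing supports that. Efficacy analyses, sample size and type I error are unaffected.

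**What to change.** 1. In 7.4.1.2, limit the bullet to Grade 4 drug-related neutropenia, lymphopenia or leukopenia, and add a line saying that Grade 4 drug-related anemia or thrombocytopenia requires discontinuation under 8.1.2, in the style the section already uses. Leave the neutropenia rule as it is.
2. Add to 7.4.1.2 the restart check from 7.4.1.3: before resuming after a delay, consult Section 7.4.2 and Section 8.
3. In 8.1, extend the reference to 8.1.1 so that it also names 8.1.2 and 8.1.3.

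Do not add a blanket sentence that Section 8 overrides 7.4.1. For sunitinib, 7.4.1.3 requires discontinuation for drug-related hemorrhage of Grade 3 or higher, while 8.1.3 stops only for Grade 4 or for Grade 3 that recurs after dose reduction; an override could displace the stricter rule. If a general sentence is wanted, it should say that dosing must not resume when any Section 8 discontinuation criterion is met, and that any stricter stop in 7.4.1 stays in force. The matching edit to the sunitinib bullet, citing 8.1.3, is optional.

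Cost: one bullet split, one added sentence and one corrected cross-reference, by amendment or clarification letter. The thresholds in 8.1.2, the design and the analyses do not change.
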